- a. Latino day laborers participating in the Brief Motivational Intervention condition will report fewer hazardous exposures at work at post-test compared to the standard-of-care control group.
- b. Latino day laborers participating in the Group Problem Solving condition will report fewer hazardous exposures at work at post-test compared to the standard-of-care control group.

AIM 2 Determine the mediating effect of psychosocial stressors on VALES+Tú primary outcomes

Research question:

a. How do situational and immigration stressors mediate the impact of the intervention program on hazardous exposures at work?

The short-term goal of VALES+Tú is to reduce LDL exposures to workplace hazards by involving them in a corner-based safety program that effectively addresses situational and immigration related stress. These psychosocial factors are seldom targeted in safety programs but evidence indicates that they increase hazardous exposures at work. Our *long-term goal* is to reduce the high rates of injury in the Latino day laborer population. If successful, we will prepare VALES+Tú for future dissemination among LDL who look for work at day labor corners in other areas of the United States with large Latino enclaves.

Activities to be conducted prior to the start of the clinical Trial

I. Rapid Needs Assessment

Prior to the implementation of the clinical trial, we will also conduct a Rapid Needs Assessment (RNA). The purpose of the RNA is to gather information related to workers' current personal characteristics, work conditions, and injury experiences. Due to the amount of time that has elapsed since the culmination of the pilot study, conducting this rapid need assessment is a critical step in ensuring our clinical trial reflects current trends and dynamics among day laborers. The RNA will be conducted with LDLs at randomly selected corners. The assessment will be administered electronically by trained interviewers using iPads. The assessment will validate psychosocial and other measures used in our previous studies as well as newly developed items. The assessment will allow us to make any necessary adjustments to our study measures before conducting the clinical trial.

RNA participant selection and Recruitment:

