Corner selection and assignment. Our recent corner needs assessment study mapped 44 corners in the Houston area bounded by the Sam Houston Tollway, covering about 350 square miles. We will base our sampling design on that number and distribution, and, prior to implementation we will survey corner sites to confirm their stability and identify new corners that may have emerged using the methodology of our Phase I pilot study. The Workers Center Outreach Coordinator will be responsible for visiting and mapping the corners. A "corner" is a) a labor hiring public location such as a street corner, bus stop, gas station or home improvement stores within the designated geographic area, b) an independent hiring site (independence as defined by at least 3 blocks of physical distance from the nearest corner), and c) a hub for day laborers observed seeking employment at that location. Locally, corners range in size from quite small (5 to 10 men) to very large (> 75 men), with the majority

supporting 12 to 30 LDL looking for work on a given day. To reach our enrollment goal of a total of 300 LDL, we plan to randomly sample 30 corners from the total number identified and select an average of 10 LDL at each corner to enroll in the study. As corner sizes vary, we may enroll fewer LDL at some corners than at others. The number of corners/clusters sampled will be kept to the sampling design of 10 per group (total of 30) to maximize statistical power.

Sample size. Sample size was estimated using Monte Carlo simulation procedures. For purposes of the simulation, we made the following assumptions: a cluster randomized design, an intervention condition at the cluster (i.e. street corner) level, 20 interventions corners, split equally across the two intervention conditions, 10 control corners, an intraclass correlation coefficient (ICC) of 0.02, an across-time correlation of outcome measures of 0.5 (derived from our pilot data), a nominal alpha of 0.05, desired power of at least 80%, three measurement waves (one pre-test and two post-test), and attrition between baseline and wave 3 of 30%. A group by time interaction serves as the primary indicator of treatment effect, with a minimum desired detectable interaction parameter estimate of 1.5 units (a value also derived from our pilot data) on the workplace hazards scale. Based on these parameters, we require an average of 10 participants from each of the 30 corners, for a total of 300 participants at baseline.

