[figure not shown]
Analyses. AIM1: Determine the efficacy of VALES+Tú in reducing hazardous exposures at work. Our primary method of longitudinal data analysis will be growth curve modeling using multilevel models (MLM). MLM is a flexible technique that can accommodate individually-varying times of observation, and time-variant and invariant variables as needed. To develop the MLM, we specify a three-level model, with repeated measures nested within individuals nested within corners, thus accounting for the clustered nature of our study design. Using matrix notation, this model takes the form y = XB + Zu+ e for continuous outcomes, where y is n x 1 vector of responses, X is the n x p design matrix of fixed effects **B**, **Z** is the n x q design matrix of random effects \mathbf{u} , and \mathbf{e} is the n x 1 vector of residual errors. Of primary interest is the two-way interaction between intervention status (intervention or control) and time located in the X vector, with random intercepts at the individual and corner levels, both located in the Z vector. The X vector will also contain important covariates as needed. The two-way interaction will indicate whether the intervention has an effect on workplace hazards during the study period, as compared to controls. Consistent with Aim 1, the two treatment groups (Brief Motivational Intervention and Group Problem Solving) will be compared separately against a common control group. Models will be estimated using maximum likelihood estimation.

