mediation analysis, which accommodates a situation where the intervention is assigned at the cluster level, but the proposed mediator and the outcome are measured repeatedly over time. A conceptual model of the proposed analysis is shown in the figure below. We will use a version of the widely accepted product of coefficients methods with bias corrected bootstrapped confidence intervals, adapted for longitudinal designs with a randomized intervention assigned at the cluster level. The product of coefficients method has been shown to have greater statistical power than the Baron and Kenny causal steps method. In the three-level operationalization of mediation analysis, two models are specified: 1) A three-level model (street corners, individuals, and repeated measurements) with the mediator as the dependent variable and intervention condition, time and the intervention by time interaction (path a) as the predictors; and 2) a separate three-level model with the outcome (e.g. workplace hazards) as the dependent variable, and intervention condition, time, the mediator (treated as a time-varying covariate; path b), and the intervention by time interaction as predictors. The product of paths a (intervention effect to mediator) and b (mediator to outcome) from model 1 and model 2, respectively, is the mediated effect. Bootstrap resampling methods are then used to compute bias-corrected 95% confidence intervals for purposes of significance testing.

Ethics

IRB approval will be sought from CPHS. State whether IRB approval will be sought from CPHS or another IRB (under UT System Reciprocity Agreement).

Study personnel will explain the nature of the study and the benefits and risks of participating. LDL will be assured that they can pause the interview if they are offered a job and resume the interview later. Consent will be sought after this process, and eligible LDL wishing to participate will signify their consent by selecting the appropriate button presented on the iPad used to present the consent form.

Data handling and record keeping

Access to source documents will be limited to the Principal Investigator and other Key Personnel. Electronic records will be stored on password protected personal computers and on the University server. Records will be retained in accordance with applicable regulations. Paper records will be stored in locked cabinets.

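### The planned arm-by-time interaction is a valid estimate but, with a free arm effect, uses the pre-test inefficiently; a common-baseline contrast would carry about 19% more information, and could be primary only if baselines are completed blind to corner assignment

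*Combined protocol and SAP*

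**What the plan says.** - **Primary contrast** (Statistics, Analyses, AIM 1): "Of primary interest is the two-way interaction between intervention status (intervention or control) and time located in the X vector". The model has random intercepts for worker and corner and is fitted by maximum likelihood. Each intervention is compared separately with the common control.
- **Other fixed effects** (same section): "The X vector will also contain important covariates as needed". The Aim 1 text does not list the main effects, does not mention the pre-test as a covariate and does not constrain the arms to a common pre-test mean.
- **Nearest full specification** (Analyses, AIM 2): the mediator model has "intervention condition, time and the intervention by time interaction (path a) as the predictors", so there the arm effect is free.
- **Hypotheses a and b** (Objectives): workers in each intervention "will report fewer hazardous exposures at work at post-test compared to the standard-of-care control group".
- **Sample size** (Statistics): "an across-time correlation of outcome measures of 0.5 (derived from our pilot data"), ICC 0.02, 10 corners per arm, 10 workers per corner on average, a "minimum desired detectable interaction parameter estimate of 1.5 units", and "three measurement waves (one pre-test and two post-test), and attrition between baseline and wave 3 of 30" per cent.
- **Number of post-tests**: one in the opening summary (Subject Duration) and in the COVID-19 Supplemental Study (Survey interview). Two in Study Design and Sample size. Study Procedures is ambiguous: it speaks of follow-up surveys in the plural, at one month, but pays for a single one.
- **Assignment and recruitment**: Study Design randomises corners. Study Procedures describes assignment after the baseline survey. Nothing says whether recruiters or workers at a corner know its arm while baselines are still being taken.

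**The concern.** With one post-test and a free arm effect, the interaction subtracts the pre-test difference between arms with weight 1. When pre-test and post-test correlate at 0.5, the weight that minimises variance is much smaller, so the planned estimate carries noise that could be removed. Randomisation justifies removing it, provided the workers enrolled in each arm are comparable at baseline.

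The number of corners is held at 10 per arm, so precision has to come from the workers and from the model. The pre-test is collected in any case. At stake is a modest but nearly free gain for hypotheses a and b. The plan also leaves open which post-test is primary and how time is coded, and the size of the gain depends on both.

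**Working it through.** **The plan's own figure.** The total of 300 is 30 corners x 10 workers. It cannot be reproduced as a power result, because the SD of the hazards scale is not given and the simulation is not shown. The information ratios below need no SD.

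**Inputs.** Total variance is set to 1. From Sample size: corner c = 0.02, across-time correlation 0.5, hence worker p = 0.48, residual 0.50 and within-corner variance w = p + 0.50 = 0.98. There are 10 corners per arm, with 10 workers per corner at pre-test. Assumptions: 7 of 10 followed at the one post-test (the plan states 30% loss only for wave 3), a corner effect that persists across waves, and a free arm effect.

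**Free-arm interaction.** Within a corner the efficient estimate of change is post(7) - b x pre(7) - (1 - b) x pre(10), with b = p/w = 0.490. The 7 followed workers' pre-tests get weight A = 0.7 + 0.3b = 0.847. The 3 lost workers' pre-tests get D = 0.3(1 - b) = 0.153. The variance per corner is

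(w/7)(1 + A²) - 2Ap/7 + D²w/3 = 0.2404 - 0.1162 + 0.0077 = 0.1319.

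Two arms of 10 corners: 0.1319 x 2/10 = 0.02638.

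**Common baseline.** This adds k times the pre-test difference, with k chosen to minimise variance.
- Variance of the pre-test corner mean: 0.02 + 0.98/10 = 0.118.
- Covariance of the change with it: (0.02 + 0.48/10) - 0.118 = -0.050.
- k = 0.050/0.118 = 0.424, so the net weight on the pre-test is 0.576 instead of 1.
- Variance per corner: 0.1319 - 0.050²/0.118 = 0.1107. For the contrast: 0.02215.

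**Ratio:** 0.02638/0.02215 = 1.19. The interaction would need about 300 x 1.19 = 357 workers to match.

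| Scenario (one post-test; correlation 0.5, ICC 0.02 and 7 of 10 followed unless stated) | Ratio |
|---|---|
| Base case | 1.19 |
| 9 of 10 followed / all followed | 1.24 / 1.27 |
| ICC 0.05 / 0.10 / 0.20 | 1.15 / 1.11 / 1.07 |
| Correlation 0.3 / 0.7 | 1.30 / 1.10 |
| Correlation 0.7 and ICC 0.20 | 1.04 |
| Corner effects independent across waves | 1.31 |

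With two post-tests the gain is 19% to 20% for the wave-3 contrast and 23% to 27% for a linear slope.

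**Power, under an assumed SD.** The pooled pilot change gives 2.0 x √63/4.26 = 3.73 for the SD of change. At correlation 0.5 this is also the outcome SD (3.73/√(2 x 0.5)).
- 7 of 10 followed: SE is 3.73 x √0.02638 = 0.606 against 0.555. Power for 1.5 units is Φ(1.5/0.606 - 1.96) = 70% against 77%.
- 9 of 10 followed: 78% against 86%.
- Three waves with 1.5 units as a per-wave slope: both above 99%, so nothing is gained.

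**Downside.** Suppose the workers enrolled in one arm truly differ by 1 unit at both waves. The interaction is unaffected. The common-baseline estimate shifts by 0.424 units, which is 0.424/0.555 = 0.76 SE. Two-sided type I error is then Φ(-1.96 + 0.76) + Φ(-1.96 - 0.76), about 12%. If the difference is adverse, power falls from 77% to 49%. An adverse difference of about 0.30 units (0.08 SD) cancels the power gain.

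**Standard errors in either model.** If corner effects are independent across waves, the interaction's variance is 0.03341, not 0.02638. A model with only a persistent corner intercept misses this. In 1,200 simulated trials with no effect, using maximum likelihood and z-tests, rejection rates for interaction and common baseline were:
- persistent corner effects, ICC 0.02: 6.1% and 6.0%;
- independent corner effects, ICC 0.02: 9.2% and 8.6%;
- ICC 0.05 with corner correlation 0.5 over time: 9.8% and 10.0%.

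**Pre-test as a covariate.** In simulation with 7 of 10 followed, a worker-level covariate alone gave SEs of 0.561, 0.611 and 0.655 at ICC 0.02, 0.10 and 0.20, against 0.606, 0.604 and 0.600 for the interaction. Adding the corner mean of the pre-test gave 0.569, 0.588 and 0.581.

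**The case against.** The strongest reply is that the planned contrast is legitimate, agrees with the sample-size basis and is robust. A difference between arms present at both waves leaves it untouched, which matters when recruitment is on street corners with no stated concealment. Blindness is doubtful in practice. About 10 workers per corner in groups of 3 to 4 means about three sessions at a group-arm corner, and interviews may be paused and finished later. Unless every baseline at a corner precedes its first session, later recruits can see the arm. This stands, and it is why the recommendation is conditional.

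Three further points also stand. The free arm effect is the ordinary reading but is inferred from Aim 2. The 19% pairs one post-test with attrition stated for wave 3 of a three-wave design; the pilot reported 88% re-contacted at about 17 days, which points nearer to 24%. And at correlation 0.7 with ICC 0.20 the gain is only about 4%.

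A reader might go further and infer that the interaction is wrong, or that 70% in the calculation refutes the planned 80% power. The documents support neither. The point estimate is valid. The 70% rests on an SD the plan does not give and on one reading of the attrition. An SD of 3.30 would give 80% with 7 of 10 followed, and reading 1.5 units as a per-wave slope gives more than 99%.

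**Conclusion.** The point holds as an efficiency improvement. Given a free arm effect, one post-test, ICC 0.02 and correlation 0.5, a common-baseline contrast carries about 19% more information with 7 of 10 followed and 24% with 9 of 10. The range is about 4% to 30% over the other inputs tried. Only the power figures depend on the assumed SD of 3.73.

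A reader might also infer that the common-baseline model should simply replace the interaction. The documents do not support that, because they do not show that baselines are taken blind to the corner's arm, and a modest imbalance would cost more than the gain. Separately, the planned random effects and maximum likelihood with 10 corners per arm can understate the standard error of either contrast if corner effects change over time.

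**What to change.** 1. Reconcile the number of post-tests across the opening summary, Study Design, Study Procedures, Sample size and the COVID-19 supplement. Name the primary time point and the time coding, and list the Aim 1 fixed effects.
2. State whether all baseline surveys at a corner are completed before recruiters and workers there know its assignment.
3. If they are, and no outcomes by arm have been seen, pre-specify as primary a mixed model with a common baseline mean across the three arms and one post-test contrast for each intervention against control. Adjustment for the pre-test that includes its corner mean is an alternative. Report the unconstrained interaction as a sensitivity analysis.
4. Otherwise keep the interaction as primary and report the baseline-adjusted model as a labelled secondary analysis. In either case say that the named primary decides hypotheses a and b.
5. In either model add a corner-by-wave random effect and a small-sample correction, for example REML with Kenward-Roger degrees of freedom. If post-tests spread over one to two months, allow for actual time since baseline, so that the individually varying times the plan values are not lost.

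**Cost.** No new data or participants. The change needs IRB approval before use. The version is dated 10/15/2021, the trial was planned for spring 2021, and the supplement refers to implementation of the parent study, so enrolment may have begun. The amendment should be dated before anyone sees outcomes by arm. The statistical price of the common-baseline model is its sensitivity to selective recruitment, which is why steps 2 to 4 are conditional. The extra random effect and the correction may widen intervals somewhat.

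### The Aim 1 model has random intercepts only, so the group-by-time test is protected against clustering only if corners do not differ in change

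*Combined protocol and SAP*

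**What the plan says.** Study Design assigns the three conditions to street corners. Under Statistics, Corner selection and assignment, there are 10 corners per condition and on average 10 men per corner, with the caveat "As corner sizes vary, we may enroll fewer LDL at some corners than at others".

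Under Statistics, Sample size: "A group by time interaction serves as the primary indicator of treatment effect". The simulation assumed an ICC of 0.02, an across-time correlation of 0.5, three waves and 30% attrition by the third. It gives one ICC. It does not say whether that ICC refers to level or change, or how corner effects correlate between waves.

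Under Statistics, Analyses, AIM 1, measures are nested in men and men in corners, "thus accounting for the clustered nature of our study design". The random part is specified "with random intercepts at the individual and corner levels, both located in the Z vector". Then: "Models will be estimated using maximum likelihood estimation". For the two hypotheses, "the two treatment groups (Brief Motivational Intervention and Group Problem Solving) will be compared separately against a common control group".

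No section gives Aim 1 a corner-by-time term, a cluster-robust standard error or corner-based degrees of freedom.

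**The concern.** A corner intercept describes how corners differ in average hazard exposure. The trial tests change. With complete two-wave data, a stable corner effect and a stable individual effect both cancel from each man's change, so the interaction test becomes a comparison of individual changes that takes no account of corner. Any change shared by men at one corner goes into the residual and is treated as independent between men.

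If such shared change exists, standard errors are too small, confidence intervals too narrow and p-values too low for both Aim 1 hypotheses. The plan cannot rule it out. The pilot had one corner per condition, so corner and condition cannot be separated there. Program content aims at cohesion and peer norms at the corner, Group Problem Solving is delivered to 3-4 men together, and the moderation analyses list corner size as a possible modifier of the group-by-time effect.

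**Working it through.** **Inputs from the documents.** ICC 0.02; across-time correlation 0.5; 10 v 10 corners per comparison; 10 men per corner at baseline, or 7 after 30% loss; nominal alpha 0.05, taken as two-sided; effect 1.5 units; pilot hazard scores 17.7 before and 15.7 after, N = 63, t = 4.26.

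**Assumed, because not stated.** The between-wave correlation of corner effects (call it c) is varied from 1 (stable) to 0. Corner variance is equal in both compared arms unless noted.

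**The plan's own figure.** The total of 300 cannot be strictly reproduced, because no outcome SD is given. The pilot implies an SD of change of 2.0 × √63 / 4.26 = 3.73. A two-wave comparison without clustering or loss then needs 2 × (1.96 + 0.84)² × 3.73² / 1.5² ≈ 97 men per arm, or 291 in total. This is close to 300 but is not evidence of how the plan's simulation was built.

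**ICC of change.** Scale the outcome variance to 1 at each wave. The variance of change is 2 × (1 − 0.5) = 1. The corner part of it is 2 × 0.02 × (1 − c) = 0.04 × (1 − c), which is also the ICC of change.

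**Design effect on the tested parameter.** DE = 1 + (m − 1) × 0.04 × (1 − c). The model's standard error is too small by 1 − 1/√DE, and type I error is about 2 × [1 − Φ(1.96/√DE)]. For example, m = 10 and c = 0.5 give DE = 1 + 9 × 0.02 = 1.18, a standard error 7.9% too small and type I error of 7.1%.

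| c | DE, m = 7 / 10 | SE too small by | Type I, formula | Type I, simulated ML with z |
|---|---|---|---|---|
| 1 | 1 / 1 | 0% | 5.0% | 5.3% |
| 0.9 | 1.024 / 1.036 | 1.2-1.8% | 5.3-5.4% | 5.7% |
| 0.8 | 1.048 / 1.072 | 2.3-3.4% | 5.6-5.8% | 6.0-6.2% |
| 0.5 | 1.12 / 1.18 | 5.5-7.9% | 6.4-7.1% | 6.9-7.6% |
| 0 | 1.24 / 1.36 | 10.2-14.3% | 7.8-9.3% | 8.2-9.7% |

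The last column is from balanced two-wave data with 100,000 null trials per cell (Monte Carlo SE at most 0.1 point). About 0.3-0.5 points of it come from assuming ML variances with a z test.

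**Unequal corners and loss.** Full three-level ML fits with 5-15 men per corner and 30% random loss (4,000 null trials per cell, Monte Carlo SE 0.3-0.5 points) gave, at c = 1 / 0.8 / 0.5 / 0:
- two waves: 5.5 / 6.1 / 7.2 / 9.5%
- three waves: 5.0 / 6.0 / 7.0 / 8.3%

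The cancellation is then not exact, but the pattern is the same.

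**Variance in the intervention arm only.** DE becomes 1 + (m − 1) × 0.04 × (1 − c) / 2. Simulated ML z type I error falls to 5.6-5.8 / 5.9-6.4 / 6.7-7.4% at c = 0.8 / 0.5 / 0.

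**Remedies, type I error.**
- A corner-by-time term fitted by ML with a z test (two waves, 30% loss) still reaches 7.7% at c = 0; with t on 18 df the figure is 5.7%. The degrees of freedom matter as well as the term.
- The same term by REML on 18 df gives 2.9-4.3%, with the variance estimated as zero in 20-54% of trials.
- A corner-level analysis of change weighted by completers, on 18 df, gives 4.5-5.3%.

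**Remedies, power.** Two waves, 1.5 units in total, SD 3.73, 5-15 men per corner, 30% loss. A test on individual changes that ignores corner has 64-65%. An unweighted corner-mean t test has 54 / 52 / 51% at c = 1 / 0.8 / 0.5, a loss of about 10 / 12 / 13 points. Weighting corners by completers cuts the loss to about 4 / 6 / 8 points.

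**The case against.** The strongest case for the plan is that the excess is small under likely conditions. The same men are surveyed again after about one month, so corner effects may well be highly correlated. At c of 0.8 or above, type I error is at most 6.2% in balanced data, and part of that rests on a z test the plan does not name. The evidence for shared change is also uneven between arms: BMI is one-on-one, controls only receive cards, and pilot cohesion rose only in the group condition. Corner size is merely an example in an exploratory moderation analysis. All of this stands and limits the size of the concern. It does not supply the missing variance, and the error, where present, runs towards false positives.

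A reader might argue that growth curve modeling, the plan's label for the method, implies random slopes. The specification names intercepts only, and a label does not add a term.

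Three stronger readings are tempting:
- A reader might infer that the clustering statement is simply false. It is not: it is sound for outcome level, and the interaction test is near nominal if corner effects are stable.
- A reader might infer type I error well above 10%. A constant ICC of 0.02 caps the ICC of change at 0.04. The simulated 13.5% requires about 0.10, which nothing in the documents supports.
- A reader might infer that the planned power is wrong. Sample size does not give the structure of the simulation, so this cannot be judged.

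**Conclusion.** The concern holds in a conditional form and should be fixed. The protection against clustering that the plan claims extends to the primary parameter only under an unstated assumption of no corner differences in change, which the pilot cannot test. The departure from 5% is negligible for stable corners, about one percentage point at c = 0.8 and 2 to 2.5 points at c = 0.5. It is 3 to 5 points at c = 0, which is unlikely for the same men after a month. These sizes rest on the plan's ICC and across-time correlation, an assumed range for c and equal corner variance in the compared arms; they are smaller if only the intervention arm varies. The conclusion does not depend on whether there are two or three waves.

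**What to change.** Keep the three-level model and add a corner-by-time random effect (a corner random slope if there are three waves). Fit by REML, and test each intervention against control on corner-based degrees of freedom: 10 + 10 − 2 = 18 per pairwise comparison. Keep the term and the degrees of freedom even if the variance is estimated as zero.

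An acceptable alternative is a corner-level analysis of change, weighted by the number of men with follow-up, on the same degrees of freedom. Choose one before the data are seen. Pooling the variance over all three arms (30 − 3 = 27 df) should be used only if equal corner variance across arms is assumed and stated. With an ICC of change of 0.04 in the group arm alone and 10 men per corner, that version gave 3.8% for BMI v control and 5.6% for Group Problem Solving v control.

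Under Sample size, state the corner-by-time variance assumed in the simulation, and restate the power if it used random intercepts only.

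The text change is short; the price is wider intervals and lower power. In the illustration above this is about 4-8 points for the completer-weighted analysis and 10-13 for an unweighted corner-mean test at c from 1 to 0.5. Part of that loss is only the stated model's excess type I error. The REML version is somewhat conservative, and its power was not computed. The illustration uses a pilot-inferred SD and does not reproduce the plan's own power.
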